### 3.3 Treatment Modifications

Dose limiting toxicities are defined as toxicities attributed to study drug administration requiring discontinuation of drug. These consist of:

- Any episode of life threatening Denileukin Diftitox hypersensitivity.
- Any grade III or IV toxicity not easily reversible to grade 1 by standard supportive measures.

In those cases where a toxicity occurs, which is deemed related to the study drug by the Principal Investigator, additional dosing may occur once the toxicity has resolved by 2 grades or to grade 1. The daily dose may be reduced to 4.5mcg/kg/day, for patients in the 9 mcg/kg/d group, or to 9 mcg/kg/d for patients in the 18 mcg/kg/d group.

Patients with life threatening hypersensitivity reactions or grade III or IV toxicity that does not resolve to grade 1, will be taken off treatment but remain on study for follow-up evaluation.

### 3.4 Protocol Evaluation

- 3.4.1 During the first cycle of intravenous treatment, patients will have electrolytes, BUN, creatinine, glucose, AST, ALT, Alkaline phosphatase, total bilirubin, LDH, albumin, total protein, calcium and phosphorous performed daily. If toxicities are no greater than grade 2 during the first cycle, metabolic profiles for subsequent cycles shall be performed every other day.
- 3.4.2 Daily weights and evaluation for peripheral edema and infection will be performed during the 5 days of treatment to monitor for vascular leak syndrome and infection.
- 3.4.3 EDTA blood (purple top tube) for surface marker studies (FACS analysis) of peripheral blood mononuclear cells is to be sent to [name] ([name], Ph: [name]). Analysis will include determination of total T- and B-cells, as well as Tac (IL-2-R $\alpha$ )-expressing T cells/mm^3. Immunofluorescence staining will be performed using CD3, CD4, CD7, CD8, and CD20, anti-Dr, anti-CD25 (either anti-Tac or BD CD25), CD45RA, CD62L, CD69, CD71 and 7G7/B6 mAbs at screening, but staining using CD3, CD4, CD7, CD8, and CD20, anti-Dr, anti-CD25 (either anti-Tac or BD CD25), a panel sufficient to assess disease burden will be done with every formal evaluation time point.
- 3.4.4 Serum samples screening for antibodies to Diphtheria toxin shall be performed at every formal evaluation time point
- 3.4.5 Serum samples for IL2R $\alpha$  soluble will be performed at every formal evaluation time point.
- 3.4.6 Complete evaluation of evaluable lesions with physical examination and appropriate X-rays / scans and biopsies will be performed after the initial 2 cycles of treatment. Stable or responding patients will continue treatment with evaluations every 4 cycles of therapy. Patients will be treated for 2 cycles beyond a complete remission.

The on study evaluations are outlined in Appendix 1 and 2

### 3.5 Concurrent Therapies:

Patients will receive empiric treatment with trimethoprim/sulfamethoxazole DS (twice daily three times weekly) unless they are allergic to this medication to prevent *Pneumocystis carinii* pneumonia (PCP). If the patient is allergic to trimethoprim or sulfamethoxazole, alternatives include dapsone (100 mg daily), atovoquone (750 mg twice daily) or inhaled pentamidine. Allopurinol therapy shall be administered at the discretion of the PI.

### 3.6 Surgical Guidelines

Standard skin or lymph node biopsies as well as bone marrow examination are permitted as required to make the diagnosis of ATL and to determine whether the malignant cells express IL-2R $\alpha$  as required in the Inclusion Criteria.

### 3.7 Skin Biopsy:

Standard 4-5 mm punch biopsies of any representative skin lesion(s) will be obtained prior to treatment in consultation with the Dermatology Branch. Biopsies will be repeated in consultation with the Dermatology Branch at the time of subsequent treatments as clinically indicated. Any patient achieving a clinical complete response (CR) will undergo repeat biopsy of a site(s) of previous known disease as part of the documentation of the CR.

### **3.8 Bone Marrow Aspirate and Biopsy:**

- 3.8.1 Diagnostic bone marrow aspirate and biopsy will be obtained prior to treatment and as clinically indicated during the course of the patient's treatment. Those patients achieving a complete response (CR) and with previous known bone marrow involvement will undergo a repeat bone marrow aspirate and biopsy as part of the documentation of the CR.

### **3.9 Lymph Node Biopsy/Aspirate:**

- 3.9.1 Patients with superficial lymph nodes deemed suspicious for involvement with tumor or those with the lymphomatous form of the disease (acute adult T-cell lymphoma) will undergo a diagnostic biopsy or aspirate prior to treatment. Biopsy specimens may be used for research purposes including but not limited to microarray analysis, establishment of cell lines, and proteomic analysis.

### **3.10 Off Treatment criteria:**

#### **3.10.1 Tumor progression**

A patient's treatment in the study will be discontinued after the first 2 cycles of Denileukin diftitox should there be evidence of tumor progression defined as a persistent (at least two determinations) doubling of the peripheral blood leukemic cell count, the development of new lesions, or Calcium elevations that are uncontrolled by conventional therapeutic procedures. Biopsies of lesions in patients with progressive disease are not routinely planned for patients on this study. If a patient shows a discordant response, a biopsy or aspirate of the involved skin or lymph node may be performed.

#### **3.10.2 Any episode of life threatening Denileukin diftitox related hypersensitivity**

- 3.10.3 Any grade III or IV toxicity not easily reversible by standard supportive measures If judged by the PI to be in the best interest of the patient.

**All patients who enter the study and discontinue their treatment early, regardless of the reason for stopping protocol treatment, will if at all possible, have a post treatment evaluation one month after the last dose of Denileukin diftitox as outlined in Section 3.12.**

### **3.11 Off Study Criteria**

- 3.11.1 Patient noncompliance or request to withdrawal from the study  
3.11.2 Tumor progression and initiation of another treatment.  
3.11.3 Completion of the protocol follow up period  
3.11.4 Death

### **3.12 Post-Treatment Evaluation (Follow-up)**

- 3.12.1 After completion or discontinuation of the study treatment, the patients will be serially followed monthly for the first three months and then at three month intervals unless the patient begins treatment for their ATL under the care of another physician.

At these interval visits, the patients will undergo the following evaluations which are described in Section 2:

- history and physical examination
- hematologic, serum studies
- sIL-2R $\alpha$
- Urinalysis
- tumor assessment
- flow cytometry

3.12.2 If clinically indicated patients shall undergo the following studies which are described in Section 2:

- skin biopsy
- skin testing.

3.12.3 Patients shall undergo apheresis on completion of therapy and the sample processed by Lab of Cellular Oncology for DNA microarray

3.12.4 After the first year the patients shall be followed every four months for the second year, every six months for the third through fifth year after completion of treatment, and then on a yearly basis.

## 4 SUPPORTIVE CARE

### 4.1 Acute Hypersensitivity

Acute hypersensitivity reactions to denileukin diftitox should be managed as outlined below. Resuscitative drugs and equipment should be readily available during administration. The dose may be reduced at the discretion of the Principal investigator.

For mild symptoms: (Localized cutaneous reactions such as mild pruritis, flushing, or rash.) Decrease the rate of infusion until recovery from symptoms, and monitor patient; complete denileukin diftitox infusion at the initial planned rate. Diphenhydramine 50 mg, may be administered at the discretion of the treating physician.

For moderate symptoms: (Any symptom not listed above (mild symptoms) or below (severe symptoms) such as generalized pruritis, flushing, rash, dyspnea, or hypotension with systolic BP >80 mmHg.) Interrupt denileukin diftitox infusion, administer diphenhydramine 50 mg i.v., and monitor patient until resolution of symptoms. Resume denileukin diftitox infusion after recovery of symptoms. At the discretion of the treating physician, denileukin diftitox infusion may be resumed at one half the initial infusion rate, then increased incrementally to the initial infusion rate. If symptoms develop after resumption of the infusion, at the discretion of the treating physician, additional oral or i.v. antihistamine may be administered. If resolution of symptoms occurs the infusion may be resumed.

For Severe Symptoms (2% of patients): Systolic blood pressure < 80 mmHg, tachycardia, chest pain or tightness, allergic reaction or anaphylaxis. Interrupt denileukin diftitox infusion, administer diphenhydramine 50 mg i.v., and monitor patient until resolution of

symptoms. If anaphylaxis or severe allergic reaction occurs, treat with corticosteroids or epinephrine, as appropriate. The infusion should be discontinued. Treatment with additional denileukin diftotox may be considered at the discretion of the Principal Investigator with steroid pre-medication in those patients whom have shown evidence of disease response.

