### **3.2 Drug Administration**

Denileukin diftitox is for intravenous (IV) use only. Treatment of patients may be administered either on an inpatient or outpatient basis. Patients receiving denileukin diftitox at either 9 or 18 mcg/kg/day for 5 days will receive their first cycle as an inpatient, but if toxicities are acceptable, subsequent dosing may be administered as an outpatient. The daily dose is to be infused over 60 minutes.

Patient's baseline weight will be used to determine all doses of Denileukin diftitox®. Dosing will be adjusted if there is a  $\pm$  10% change in weight.

Patients will be premedicated with acetaminophen (650 mg po) and diphenhydramine (25-50 mg po), 30-90 minutes prior to each infusion and PRN for symptoms. Meperidine (25-50 mg IV) may be given if chills or rigors develop.

Patients will be monitored with vital signs (temperature, pulse, respiration and blood pressure) before and every 15 minutes during the Denileukin diftitox infusion, and then every 30 minutes for a total of 2 hours after the infusion.

Some patients may develop tumor lysis syndrome. If the patient is considered at risk for tumor lysis syndrome; allopurinol, hydration and alkalinsiation will be administered according to the discretion of the Principal Investigator.

The most common side effects observed are elevated transaminases, hypoalbuminemia, vascular leak syndrome, fatigue and flu-like symptoms. These side effects tend to occur less frequently with further cycles.

If infusional adverse reactions occur, the infusion should be discontinued or the rate should be reduced depending on the severity of the reaction (see Section 4.1). Denileukin diftitox dose may be modified at the discretion of the principal investigator. If the patient is unable to tolerate the 9mcg/kg/day dose it may be reduced to 4.5mcg/kg/day. If the patient is unable to tolerate the 18 mcg/kg/day dose it may be reduced to 9 mcg/kg/d. Allergic reactions to dose administration are possible, therefore appropriate drugs and medical equipment to treat acute anaphylactic reactions must be immediately available and study personnel must be trained to recognize and treat anaphylaxis. If symptom of moderate (grade 2) or severe (grade 3) hypersensitivity persist for longer than 6 hours despite treatment of symptoms, further treatment with Denileukin diftitox should be discontinued. If anaphylaxis occurs at any time, further treatment with Denileukin diftitox must be discontinued.

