### 5.4 Statistical Section

5.4.1 This study will include patients diagnosed with chronic, lymphomatous or acute ATL. Full lists of inclusion and exclusion criteria are presented in Section 2.2 and 2.3.

5.4.2 We will use an optimal two-stage design {Simon, 1989} to test for early evidence for efficacy based on complete and partial response. The design is based on the following: (a) the response proportion (partial and complete response) will be less than 5% if the treatment is totally ineffective ( $P_0=0.05$ ), (b) the treatment will be considered effective and worthy of future investigation if the true response proportion is  $> 30%$  ( $P_1=0.30$ ), (c) a type I error rate of 5% (i.e., the probability of concluding that the treatment is effective if the true response rate is 5% is 0.05), (d) a power of 95% (i.e., the probability of concluding that the treatment is effective if the true response proportion is 30% is 0.95).

In the first stage of the two-stage design, nine patients will be studied. If there are no partial or complete responses observed among the initial nine patients treated with a dose of 9 mcg/kg/d, the study will be expanded to an additional 9 patients at a dose of 18 mcg/kg/d. If one or more of the nine patients respond at either dose level, the study will proceed to a second stage. An additional 20 patients (i.e., a total of 29 patients in the trial) will be studied in the second stage at the same dose level. If four or more out of the 29 patients respond, the treatment will be deemed effective in early phase II development. The treatment will be deemed ineffective if fewer than four respond out of 29 patients.

With this design, there is a 63% chance of proceeding to the 18 mcg/kg/dose, if the response rate at 9 mcg/kg.dose is an ineffective 5%. Similarly, there is a 63% chance of terminating the study if the response rate at 18 mcg/dose/day is 5%.

The major objective of this study is to determine the anti-tumor activity of Denileukin diftitox with regard to response rate, time to progression, and overall survival. Response rate will be based on the number of patients who achieve either a complete or partial response to therapy. Time to progression will be measured from the date of registration until documentation of disease progression. Overall survival will be determined from the date of registration to the event of death or, for surviving patients, censored by the last day patients are known alive.

5.4.3 Antitumor Efficacy:

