## **7 DATA AND SAFETY MONITORING PLAN**

This protocol does not require a DSMB. The Principal Investigator shall monitor the trial by meeting on a monthly basis with the clinical trial team. The regulatory documents and Case Report Forms (CRFs) will be reviewed to verify adherence to good clinical practice procedures and to the protocol. The completeness, consistency and accuracy of the data entered on the CRFs shall be monitored. Copies of protocols, CRFs, original documentation of test results, correspondence, records of informed consent and other documents pertaining to the study will be kept on file in agreement with national regulation. The Principal Investigator is responsible for the safety and welfare of patients under their care and prompt identification, assessment and reporting of adverse events in accordance with protocol requirements. Safety data will be reviewed at other time points in response to adverse events felt to be medically significant.

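### Section 4.1 lets the Principal Investigator consider more drug for a responder after a severe reaction without excluding the hypersensitivity events for which Sections 3.2, 3.3 and 3.10.2 stop treatment

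*Combined protocol and SAP*

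**What the plan says.** Section 4.1 sorts acute reactions into mild, moderate and severe. The severe tier comprises systolic pressure below 80 mmHg together with "tachycardia, chest pain or tightness, allergic reaction or anaphylaxis". It gives the acute treatment, including corticosteroids or epinephrine for anaphylaxis, and says the infusion should be discontinued. Its last sentence reads: "Treatment with additional denileukin diftotox may be considered at the discretion of the Principal Investigator with steroid pre-medication in those patients" with evidence of disease response.

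Three other places set stopping rules:

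- Section 3.2: "If anaphylaxis occurs at any time, further treatment with Denileukin diftitox must be discontinued". The sentence before it says treatment should be discontinued if grade 2 or grade 3 hypersensitivity lasts more than 6 hours despite treatment of symptoms.
- Section 3.3: "Patients with life threatening hypersensitivity reactions or grade III or IV toxicity that does not resolve to grade 1, will be taken off treatment".
- Section 3.10.2, among the off-treatment criteria: "Any episode of life threatening Denileukin diftitox related hypersensitivity".

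None of the three makes an exception for responders. Section 3.2 refers the reader to Section 4.1 for handling infusion reactions. Section 4.1 does not refer back, and no sentence says which section governs.

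**The concern.** The permission in Section 4.1 comes directly after the instructions for anaphylaxis and, as worded, covers the whole severe tier. A responder with anaphylaxis therefore falls under both a permission and a prohibition. The same holds for a life-threatening reaction of another kind, and for severe hypersensitivity that outlasts 6 hours of treatment.

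The overlap falls on the patient for whom the case for continuing is strongest, and re-exposure after anaphylaxis can be fatal. The timing is plausible. Response is first assessed after two cycles (Sections 1.2.8 and 3.1), and Section 10.1.6 reports that about half of acute reactions fell on the first dosing day whatever the cycle. A first severe reaction can therefore follow a known response.

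**Working it through.** **Text comparison, by event in a responder**

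| Event | Section 4.1 | Stopping rule |
|---|---|---|
| Anaphylaxis | In the severe tier; more drug may be considered | Section 3.2: must stop |
| Other life-threatening hypersensitivity, if it meets the severe tier | More drug may be considered | Sections 3.3 and 3.10.2: off treatment |
| Grade 2 or 3 hypersensitivity lasting over 6 hours despite treatment, if it meets the severe tier | More drug may be considered | Section 3.2: should stop |
| Other severe-tier reactions that resolve | More drug may be considered | None specific to hypersensitivity |

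The first three rows overlap; the fourth does not. The permission therefore has a proper use once the first three are taken out.

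**How often the anaphylaxis case could arise**

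Inputs:

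- Section 10.1.6: 98 of 143 earlier patients had acute hypersensitivity-type reactions, and anaphylaxis occurred in 1% of those 98. So p = 0.01 × 98 / 143 = 0.685%, about one case.
- Section 5.4.2: response rate r = 0.05 (P0) or 0.30 (P1); nine patients in stage one, 20 more if at least one responds.

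The plan's own figure comes first. The chance of no response in nine at r = 0.05 is 0.95^9 = 0.630, which reproduces the stated 63% chance of ending the study at 18 mcg/kg/d.

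The chance that one patient is a responder with anaphylaxis, under independence, is p × r. Let S = (1 − r)^9 be the chance of stopping after stage one, A = (1 − pr)^9 the chance of no such patient in the first nine, and B = (1 − pr)^20 the same for the next 20. If stage one has no responder, the event cannot occur and the cohort stops. So

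P(at least one) = 1 − [S + (A − S) × B].

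- r = 0.05: pr = 0.000343, S = 0.6302, A = 0.9969, B = 0.9932. P = 1 − [0.6302 + 0.3667 × 0.9932] = 0.56%.
- r = 0.30: pr = 0.002056, S = 0.0404, A = 0.9816, B = 0.9597. P = 1 − [0.0404 + 0.9412 × 0.9597] = 5.6%.

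Treating all 29 patients as certain to be enrolled gives 1 − (1 − pr)^29 = 0.99% and 5.8%. The first-stage stop matters at 5% and hardly at 30%.

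**Uncertainty in p.** The exact 95% interval for 1 of 143 is 0.018% to 3.83%. Put through the same two-stage formula, it gives about 0.015% to 3.0% at r = 0.05 and 0.15% to 28% at r = 0.30. Appendix 5 lists no allergic reaction or anaphylaxis among the nine patients at 9 mcg/kg/d. Zero of nine excludes only rates above 1 − 0.025^(1/9) = 34%, so it does not help.

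**The case against.** The strongest reply is that both rules can be obeyed. Section 3.2 is specific and mandatory; Section 4.1 is permissive. An investigator who stops after anaphylaxis breaches nothing in Section 4.1, while one who re-treats breaches Section 3.2. On ordinary reading a specific prohibition limits a general permission, and the permission still serves the other severe-tier reactions. This stands as a reasonable and probably intended reading. It means a reader who infers that the protocol authorises re-treatment after anaphylaxis goes too far, because the stop in Section 3.2 remains in force. It does not remove the defect. The protocol never states that precedence, Section 3.2 itself sends the reader to Section 4.1, and a permission limited to responders can equally be read as an exception to the general stop.

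A reader might also infer that oversight is lacking, since Section 7 says "This protocol does not require a DSMB". That adds little. The documents give no such board a role in individual re-treatment decisions. Other controls exist: Section 9.2.1 has protocol violations and deviations reported to the IRB within 7 working days. Section 5.4.4 counts related toxicity of grade 4 or greater in the first 28 days toward a stopping rule and puts accrual on hold after two drug-related deaths.

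The size can be challenged too. The two-stage calculation above meets the objection that 29 patients are not assured. Two limits remain. The calculation counts anaphylaxis in any eventual responder, although the overlap needs evidence of response to come first, so on that account the figures are too high. And Section 10 speaks, for Amendment G, of a single patient currently on study, dosed under an attached section that is not in the documents. Whether accrual continues, and whether that attachment covers reactions, cannot be told.

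**Conclusion.** The inconsistency is real and concerns patient safety. Section 4.1 grants a permission whose wording includes anaphylaxis, other life-threatening hypersensitivity, and prolonged grade 2 or 3 hypersensitivity that meets its severe tier. Other sections stop treatment in each of these. A reading that reconciles them is available but not written down.

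The anaphylaxis case is rare: about 0.6% over the 18 mcg/kg/d cohort at a 5% response rate and about 6% at 30%. This assumes that the earlier rate carries over to 18 mcg/kg/d every two weeks, that anaphylaxis is independent of response, and that evidence of response means a complete or partial response. Section 4.1 does not define that phrase; a looser meaning would bring in more patients. With about one earlier case, the rate is poorly known, and the 28% upper figure combines the upper confidence limit with the design's target response rate. The documents do not support figures for the other two overlaps.

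A reader might infer consequences for the efficacy analysis. The documents give no ground for that: the two-stage design, response count, sample size and error rates are untouched.

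**What to change.** At the end of the last sentence of Section 4.1, add: , except after anaphylaxis, any life-threatening hypersensitivity, or grade 2 or 3 hypersensitivity persisting longer than 6 hours despite treatment, after which no further denileukin diftitox is given, whatever the response (3.2, 3.3, 3.10.2).

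Keep the limit to patients with evidence of response, and keep the permission for the remaining severe-tier reactions.

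The cost is one clause by amendment and a notice to investigators, with no new data, procedures or patients. For anaphylaxis and life-threatening hypersensitivity it withholds only what Sections 3.2, 3.3 and 3.10.2 already withhold. For reactions lasting over 6 hours it turns the advisory wording of Section 3.2 into a firm stop, so that sentence of Section 3.2 should be worded to match.
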